6.3 Dose modification and Dose delay

ARM A: REGIRI

Regorafenib: Dosage changes should be made in 40 mg increments (1 tablet). The recommended daily dose of Regorafenib is 160 mg.

Dose reductions of Regorafenib	
1 st reduction: 120 mg	
2 nd reduction: 80 mg	

Table a*

Digestive toxicity: Diarrhea

A symptomatic treatment of the diarrhea occurring more than 24 hours after the irinotecan administration is possible by diosmectite (Smecta®), 1 sachet/8h and loperamide (Imodium®), 2 capsules/8h until 24 hours after the last stool which is loose or watery. If, in spite of this treatment, the diarrhea is not under control in the first 24 hours then fluoroquinolones as antibiotics will be orally given during 7 days.

In case of diarrhea > grade 1, the patient will receive during the next courses of treatment a prophylactic treatment by sucralfate (Keal®) 1 sachet / 6 h et Ercefuryl® 200 at a rate of 3 capsules/24 h.

Table 1: Action and dose modification during the administration of Irinotecan and Regorafenib after the first course of treatment in case of diarrhea

Protocole NEXT-REGIRI -Version 6.0 du 09/11/2023

Page **41** sur **86**

Grade	During the course of treatment	dose at the next course of treatment
Grade 1	NA	Irinotecan at 150 mg/m². Regorafenib at 160 mg per day + prophylactic treatment
Grade 2	Interrupt irinotecan until diarrhea resolves to Grade ≤ 1	Irinotecan at 120 mg/m². Regorafenib at 160 mg per day + prophylactic treatment
Grade 3	Interrupt irinotecan until diarrhea resolves to Grade ≤ 1	Irinotecan at 120 mg/m² and Regorafenib at 120 mg per day
Grade 4	Discontinue treatment permanently	Discontinue treatment permanently

Table 2: Action and dose modification during the administration of Irinotecan and Regorafenib after the second course in case of diarrhea

Grade	During the course of	Dose at the third course of	
Grade	treatment	treatment	
		Dose-escalation of irinotecan is	
Grade 1	NA	permitted. Regorafenib at 160	
Grade I	INA	mg per day	
		+ prophylactic treatment	
		Dose-escalation of irinotecan is	
Condo 2	Interrupt irinotecan until diarrhea resolves to Grade	not permitted. Regorafenib at	
Grade 2	≤ 1	160 mg per day	
		+ prophylactic treatment	
	1st accurrance: Interrupt	1st occurrence: Decrease	
Grade 3	1st occurrence: Interrupt irinotecan until diarrhea	Irinotecan to 120 mg/m².	
	resolves to Grade ≤ 1	Regorafenib to 160 mg per day	

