	2 nd occurrence: Interrupt irinotecan until diarrhea resolves to Grade ≤ 1	2 nd occurrence: Irinotecan dose is not changed at 120 mg/m² and decrease Regorafenib to 120 mg per day
	3rd occurence : Discontinue treatment permanently	3rd occurence : Discontinue treatment permanently
Grade 4	Discontinue treatment permanently	Discontinue treatment permanently

Table 3: Action and dose modification during the administration of Irinotecan and Regorafenib after the third course and beyond in case of diarrhea

	Grade	During the course of treatment	Dose at the third course of treatment
Grade 1-2		Interrupt irinotecan until diarrhea resolves to Grade ≤ 1	No dose modification + prophylactic treatment
Grade 3	Patients having	 1st occurrence: Interrupt irinotecan until diarrhea resolves to Grade ≤ 1 2nd occurrence: Interrupt irinotecan until diarrhea resolves to Grade ≤ 1 	1st occurrence: Decrease Irinotecan to 150 mg/m². Regorafenib to 160 mg per day 2nd occurrence: Decrease Irinotecan to 120 mg/m². Regorafenib to 160 mg per day
	received the irinotecan dose of 180 mg/m2	3 rd occurence : Interrupt irinotecan until diarrhea resolves to Grade ≤ 1	3 rd occurrence: Irinotecan is not changed at 120 mg/m² and decrease Regorafenib to 120 mg per day

		4th occurence : Discontinue treatment permanently	4th occurrence: Discontinue treatment permanently
		1 st occurrence: Interrupt irinotecan until diarrhea resolves to Grade ≤ 1	1st occurrence: Decrease Irinotecan to 120 mg/m². Regorafenib to 160 mg per day
	Patients having received the irinotecan dose of 150 mg/m²	2 nd occurrence: Interrupt irinotecan until diarrhea resolves to Grade ≤ 1	2 nd occurrence: Irinotecan is not changed at 120 mg/m² and decrease Regorafenib to 120 mg per day
	3rd occurence : Discontinue treatment permanently	3rd occurence : Discontinue treatment permanently	
	Patients having received the irinotecan dose of 120 mg/m²	1st occurrence: Interrupt irinotecan until diarrhea resolves to Grade ≤ 1	1st occurrence: Irinotecan is not changed at 120 mg/m² and decrease Regorafenib to 120 mg per day
		2nd occurrence: Discontinue treatment permanently	2nd occurrence: Discontinue treatment permanently
Grade 4		Discontinue treatment permanently	Discontinue treatment permanently

Hematologic toxicity

Table 4: Action and dose modification during the administration of Irinotecan in case of hematologic toxicity

CBC at D15	Delayed Treatment	Decrease the dose for the next courses of treatment

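### In arm A, eight diarrhoea rows of Tables 1-3 fix regorafenib at 160 mg per day, so read literally they can raise a dose already cut to 120 mg

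*Combined protocol and SAP*

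**What the plan says.** Arm A starts regorafenib at 160 mg. Table a allows two reductions, to 120 mg and then 80 mg, and section 6.3 opens by requiring changes in steps of one 40 mg tablet.

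Diarrhoea has its own tables: Table 1 after course 1, Table 2 after course 2, Table 3 from course 3 on. They give regorafenib mostly as an absolute dose:

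- Table 1, grade 3: "Irinotecan at 120 mg/m² and Regorafenib at 120 mg per day". Grades 1 and 2 state 160 mg.
- Table 2, grade 1: irinotecan escalation is "permitted. Regorafenib at 160" mg per day. Grade 2 bars the escalation but states the same regorafenib dose. A first grade 3 event also states 160 mg.
- Table 3, first grade 3 event at irinotecan 180 mg/m²: "Decrease Irinotecan to 150 mg/m². Regorafenib to 160 mg per day".
- Table 3, first grade 3 event at irinotecan 150 mg/m²: "Decrease Irinotecan to 120 mg/m². Regorafenib to 160 mg per day". The second event in the 180 mg/m² block uses the same words.
- Table 3, grade 1-2: "No dose modification + prophylactic treatment". This is the only continuing row that keeps whatever dose the patient is on.

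Tables 5 to 9 cover the other arm A toxicities and lower regorafenib relative to the current dose, by one level or one tablet. Re-escalation appears only in Table 7 note b (hand-foot skin reaction) and Table 8 note b (hypertension). The arm A text of 6.3 has no sentence on which table prevails when two of them give different regorafenib doses.

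**The concern.** An absolute 160 mg is harmless while the patient is still on full dose. Once the dose has been reduced to 120 mg, the same words tell the site to go up. The trigger is a new toxicity, and in the simplest case it is a recurrence of the toxicity that caused the reduction.

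Two things are at stake in arm A. One is safety: regorafenib is raised in someone whose earlier grade 3 diarrhoea, liver or haematological event called for the lower dose. The other is conduct: sites in a multicentre trial could dose identical patients differently, and either choice could be called a deviation.

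**Working it through.** **Row count.** These are the rows in which treatment continues, classified by the stated regorafenib dose.

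| Table | Continuing rows | 160 mg | 120 mg | Unchanged |
|---|---|---|---|---|
| 1 | 3 | 2 | 1 | 0 |
| 2 | 4 | 3 | 1 | 0 |
| 3 | 7 | 3 | 3 | 1 |
| Total | 14 | 8 | 5 | 1 |

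In Tables 2 and 3 together, 3 + 3 = 6 of 4 + 7 = 11 rows state 160 mg. Of those six, two follow grade 1 or 2 diarrhoea and four follow grade 3.

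**Size of the step.** From 120 mg, 160 - 120 = 40 mg and 160/120 = 1.33, so +33%. This is one 40 mg increment, and the opening sentence of 6.3 does not block it.

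**Can a patient at 120 mg reach these rows?**

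1. *Table 2, grades 1 and 2 (diarrhoea tables alone).* Grade 3 diarrhoea after course 1 gives irinotecan 120 mg/m² and regorafenib 120 mg. Grade 1 or 2 after course 2 then states regorafenib 160 mg, and at grade 1 irinotecan may rise too. With no diarrhoea after course 2, no rule raises regorafenib and the patient stays at 120 mg. The same grade after course 3 falls in the unchanged row of Table 3. The worse course thus gets the higher regorafenib dose, and only at this one time point.
2. *Table 3, first grade 3 at irinotecan 150 mg/m².* A first grade 3 ALT/AST rise after course 2 interrupts regorafenib. If the values recover and the benefit is judged to outweigh the risk, Table 9 restarts it one tablet lower, at 120 mg. Section 6.1 withholds irinotecan 180 mg/m² after such a toxicity, so irinotecan stays at 150. A first grade 3 diarrhoea then states 160 mg. Table 9 has no re-escalation provision.
3. *Table 3, first grade 3 at irinotecan 180 mg/m².* Grade 3 neutropenia at D15 with platelets above 100 000/mm³ leaves irinotecan unchanged with G-CSF (Table 4) and takes regorafenib down one level to 120 mg (Table 5). A first grade 3 diarrhoea then states 160 mg. Table 5 has no re-escalation provision either.
4. *Table 2, first grade 3.* This row lowers irinotecan to 120 mg/m², so it assumes a higher current dose. It does not fit a patient already at 120 mg/m² from Table 1 grade 3. A conflict needs a separate regorafenib reduction in the same course.
5. *Table 3, second grade 3 in the 180 mg/m² block.* Read literally, the first event has already set 160 mg, so the second changes nothing. A conflict needs a separate reduction between the two diarrhoea events.
6. *Table 1, grades 1 and 2.* Course 1 starts at 160 mg, so these rows conflict only with a reduction made during course 1.

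Four of the six 160 mg rows in Tables 2 and 3 therefore have a plain route from 120 mg (items 1 to 3), and two need an additional coinciding reduction (items 4 and 5).

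**The case against.** The best defence is intent. The ladder starts at full dose and generally lowers irinotecan before regorafenib, so 160 mg in a cell most naturally means that regorafenib is not reduced at this step. Where the protocol wants a dose raised it says so and sets conditions, as in the notes to Tables 7 and 8. The heading of Table 6 excludes diarrhoea, liver tests, hypertension and hand-foot reaction, which suggests that each toxicity has its own table and that a diarrhoea row was never meant to cancel a liver or blood-count reduction. The safety committee also reviews two-month safety in arm A after the first twenty patients.

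Most of this stands as a reading of intent, and it is why the point is modest. It does not remove the conflict. The drafters had wording for an unchanged dose and used it once, in Table 3 grade 1-2. Because Table 6 excludes diarrhoea, Tables 1 to 3 are the only regorafenib rule a site has for this toxicity. The Table 1 to Table 2 sequence involves no second toxicity, so allocating toxicities to separate tables does not resolve it. A single scheduled safety review does not correct dosing text.

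Two softer points also stand. After hand-foot reaction or hypertension a return to 160 mg may be legitimate, so the conflict is weaker there. Table a carries an asterisk with no visible note, and a limiting footnote lost in extraction cannot be excluded.

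**Conclusion.** The point holds as a modest safety and conduct correction in arm A. Eight of 14 continuing rows state an absolute 160 mg. For a patient at 120 mg the literal effect is +40 mg (+33%), shown by a plain route for four rows: Table 2 grades 1 and 2, and the first grade 3 rows of Table 3 at irinotecan 150 and 180 mg/m².

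This rests on a literal reading, on no limiting note being attached to Table a, and, for the 180 mg/m² row, on Table 4 governing irinotecan after neutropenia.

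A reader might infer more than the documents support:

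- *That all six rows in Tables 2 and 3 are reached by these routes.* Two are not, for the reasons in items 4 and 5 of the working.
- *That a patient at 80 mg would be doubled to 160 mg.* That is two 40 mg steps, so the increment rule does not let it through as it does the rise from 120 mg.
- *That a number of affected patients can be given.* The protocol has no REGIRI event rates and no joint rates. The Background figures of 40% neutropenia and 14% diarrhoea (grade 3 or higher) are for regorafenib with FOLFIRI in second line, a different regimen and setting.
- *That the trial's main result is affected.* The sample size and the overall survival analysis do not depend on this wording.

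**What to change.** In the eight rows, replace the fixed 160 mg with: *continue regorafenib at the current dose level*. Add to section 6.3, arm A: *The diarrhoea tables never raise regorafenib; when several tables apply, the lowest resulting dose governs, and re-escalation is allowed only under Table 7 note b or Table 8 note b.*

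Leave the five 120 mg rows unchanged. Some of their wording is awkward for a patient at 80 mg, for example "Irinotecan dose is not changed at 120 mg/m² and decrease Regorafenib to 120 mg per day". Turning them into one-level reductions, however, would send some patients from 120 to 80 mg, such as one with a second grade 3 event in Table 2 after grade 3 in Table 1. That would be a new dosing rule and needs a clinical decision of its own.

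The cost is eight table cells and one sentence in a protocol amendment, with notice to sites. Data collection, sample size and analysis do not change.

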ANC < 1500/mm ³	J21*	No dose modification + G-CSF

Protocole NEXT-REGIRI -Version 6.0 du 09/11/2023

Page **44** sur **86**

and Platelets > 100 000/mm ³		
Platelets < 100 000/mm ³	121*	Padusa by 1 dosa laval
Whatever the number of ANC	JZ I"	Reduce by 1 dose level

^{*} or until 28th day as needed (maximum)

Modalities of Reintroduction of treatment : ANC \geq 1500/mm³ and Platelets \geq 100 000/mm³ If the Platelets and/or ANC values are not correct at D28, the patient will discontinue permanently the study treatment.

At the time of Nadir

In the case of a grade 4 neutropenia, whatever the duration or complication i.e by an infection or fever > 38°5, the G-CSF will be administered at the next course of treatment. If the same toxicity continues with G-CSF then the irinotecan dose will be reduced at the dose immediately inferior. If there is a third occurrence of this toxicity, the patient will permanently discontinue the study treatment.

Table 5: Action and dose modification during the administration of Regorafenib in case of hematological toxicity

Hematological toxicity (Modification dose/delay for Regorafenib)			
Grade	Treatment delay	Dose modification	
Grade 0-2	No delay in Regorafenib	No modification dose	
Grade 0-2	treatment	No modification dose	
Grade 3	No delay in Regorafenib	Reduce by 1 dose levelbc	
Grade 3	treatment	heduce by Tuose level	
	Interrupt Regorafenib		
Grade 4	until hematologic	Reduce by 1 dose level ^{bc}	
	toxicity resolves to	heduce by Tuose level	
	Grade ≤ 2ª		

a If no recovery within 30 days, the treatment will be permanently discontinued.

- b If more than 2 dose reductions are necessary, the treatment will be permanently discontinued.
- c Cf table a.

Table 6: Action and dose modification during the administration of Regorafenib in case of non-hematologic toxicity

Non-hematological toxicity (dose modification/delay for Regorafenib) (except hand-foot skin reaction, hypertension, liver function test abnormalities and diarrhea)^a

Grade	Treatment delay	Dose modification
Grade 0-2	No delay in Regorafenib treatment	No dose modification
Grade 3	Interrupt Regorafenib until non hematologic toxicity resolves to Grade ≤ 2 ^b	Reduce by 1 dose level ^{cd}
Grade 4	Discontinue treatment permanently	Discontinue treatment permanently

- a In the absence of nausea/vomiting prophylaxis and diarrhea not treated.
- b If more than 2 dose reductions are necessary, the treatment will be permanently discontinued.

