8.1. DISCONTINUATION OF TREATMENT

Discontinuation of treatment does not represent withdrawal from the trial. As certain data on clinical events beyond treatment discontinuation are important to the study, they must be collected through the subject's last scheduled follow-up, even if the subject has discontinued treatment. Therefore, all subjects who discontinue trial treatment prior to completion of the treatment regimen will still continue to participate in the trial.

Patient may be discontinued from study treatment at any time if the patient, the Investigator, or the Sponsor feels that it is not in the patient's best interest to continue on study. The following is a list of possible reasons for early discontinuation of study treatment:

- Disease progression (unless there is reasonable evidence of clinical benefit to justify continuation on treatment – to be discussed with the Sponsor)
- In the investigator's opinion, continuation in the study treatment would be detrimental to the patient's well-being
- Protocol violation requiring discontinuation of study treatment
- Patient is not compliant with study procedures
- Patients with a β-HCG test consistent with pregnancy. Pregnancy will be reported as a serious adverse event.
- Any adverse event that cannot be adequately managed with dose modifications, including dose interruption > 28 days (unless there is reasonable evidence of clinical benefit to justify continuation on the protocol – to be discussed with the Sponsor)
- Discontinuation of treatment during more than 4 weeks
- Patient death
- New cancer
- Lost to follow-up

(The Investigators should make every effort to recontact the patient to identify the reason why he/she failed to attend the visit, and to determine the patient health status, including at least the vital status. Attempts to contact such patients must be

documented in the patient's records (e.g., times and dates of attempted telephone contact, receipt for sending a registered letter).

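### Arm A: if blood counts are still low at D28, Table 4 stops study treatment permanently while Table 5 lets regorafenib continue or resume

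*Combined protocol and SAP*

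**What the plan says.** Three places in the protocol set or suggest a time limit for arm A.

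- **Section 6.3, Table 4**, titled "Action and dose modification during the administration of Irinotecan in case of hematologic toxicity". It is triggered by the D15 count: neutrophils below 1500/mm³ or platelets below 100 000/mm³. The next infusion is put back to day 21, or to day 28 at the latest. Restarting needs both counts at or above those limits. Otherwise: "If the Platelets and/or ANC values are not correct at D28, the patient will discontinue permanently the study treatment".
- **Section 6.3, Table 5**, titled "Action and dose modification during the administration of Regorafenib in case of hematological toxicity". For Grades 0-2 there is neither delay nor dose change. For Grade 3 there is no delay and the dose drops one level. For Grade 4 the drug is interrupted until Grade 2 or better and the dose drops one level, with this note on the interruption: "If no recovery within 30 days, the treatment will be permanently discontinued". Another note stops treatment if more than two reductions would be needed. Table 6 (non-haematological toxicity) has the same 30-day note.
- **Section 8.1** lists possible reasons for stopping early. One is "Any adverse event that cannot be adequately managed with dose modifications, including dose interruption > 28 days", with an exception for clinical benefit to be discussed with the sponsor. Another is "Discontinuation of treatment during more than 4 weeks", with no exception.

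Nothing in the protocol ranks these rules.

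**The concern.** Tables 4 and 5 cover the same patient and the same kind of toxicity, and both are written as instructions rather than suggestions. If counts have not recovered by D28, a site that follows Table 4 literally withdraws both drugs for good. A site that follows Table 5 carries on with regorafenib or waits to resume it. Both have followed the protocol.

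This decides who permanently loses experimental treatment, in an arm planned at 39 patients. It also reaches the data. The date of stopping treatment can differ between sites for identical patients. Time to deterioration (section 2.2.2) counts only a performance-status decline that occurs while on treatment, so its observation window moves with that date. The per-protocol population (section 9.2) excludes patients with major deviations affecting efficacy assessment. With two conflicting rules, the same conduct could be classed as compliant or as a deviation.

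**Working it through.** No sample size, power or error rate enters here, and the plan gives no figure to reproduce. The check sets the rules side by side and counts days.

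**Inputs.** Table 4: count at D15, last date D28. Table 5: 30 days, Grade 4 only. Section 6.1: in arm A irinotecan is due on days 1 and 15, and regorafenib is taken on days 2-8 and 16-22. Section 8.1: 28 days, and 4 weeks. Days are counted from the infusion whose D15 count is low, taken as the first of a cycle.

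**Step 1, Table 4's clock.** 28 − 15 = 13 days after the next infusion was due. D28 is therefore a day number and not a 28-day recovery period.

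**Step 2, the two tables at D28 with counts still below Table 4's limits.**

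| Grade at D28 | Table 4 | Table 5 (regorafenib) |
|---|---|---|
| Up to 2 | Permanent stop of study treatment | No delay, same dose |
| 3 | Permanent stop of study treatment | No delay, one level lower |
| 4 | Permanent stop of study treatment | Interrupt; stop only if not recovered within 30 days |

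The grade cut-offs are not in the text supplied, but they are not needed, because Table 5 answers for every grade. The tables can agree in one case: a patient already reduced twice who would need a third reduction is stopped by Table 5's note on the number of reductions.

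**Step 3, can Table 5's 30 days run out by D28?** An interruption starting on day s runs to day s + 30. The excess over D28 is s + 30 − 28 = s + 2.

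| Clock starts (assumed) | 30 days end | Days after D28 |
|---|---|---|
| D2, first regorafenib day | D32 | 4 |
| D8, last day of the first block | D38 | 10 |
| D15, the low count | D45 | 17 |
| D16, first dose withheld after that count | D46 | 18 |

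For the period to end by D28, s would have to be −2 or earlier, before the infusion from which the days are counted. No interruption that begins after that infusion can reach its limit by D28. A Grade 4 patient who recovers between D29 and the end of the period is stopped by Table 4 and resumes at a lower dose under Table 5.

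**Step 4, Tables 5 and 6 against section 8.1.** 4 weeks × 7 = 28 days, so the two reasons in section 8.1 have the same length and differ in the exception. 30 − 28 = 2 days: a patient recovering on day 29 or 30 may resume under the tables but meets both listed reasons in section 8.1.

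**The case against.** The best defence is that the tables govern different drugs. Table 4 is headed for irinotecan, and its 13 days sit close to the two-week irinotecan delay allowed under Other toxicities in the same section. If its stop were meant for irinotecan alone, Tables 4 and 5 would not conflict. The heading does support this, and the term study treatment is undefined. But the stopping sentence is not limited to irinotecan. The paragraph on the nadir that follows speaks of reducing the irinotecan dose and then, separately, of ending study treatment, so the authors use the two terms differently. Where regorafenib alone is to stop, Tables 8 and 9 name it. If irinotecan alone was intended, the text still has to say so.

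On section 8.1 the defence largely succeeds. The list is permissive, one item concerns adverse events and the other interruption in general, and the difference from the tables is 2 days.

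Three stronger readings are tempting and are not supported:

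- **A 17-day gap for anyone with low counts at D15.** The 30 days apply to Grade 4 only, and 17 days assumes a clock starting on D15, a day on which arm A takes no regorafenib.
- **Unfair limits between arms.** Arm B's Table 10 uses 4 weeks against 30 days, again 2 days. It excludes asymptomatic laboratory abnormalities, the regorafenib schedules differ, and both arms share the same limit for hypertension (Tables 8 and 12). Equal limits are not required.
- **A threat to the primary result.** Section 8.1 keeps patients who stop treatment in follow-up, and overall survival is analysed in all randomized patients.

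**Conclusion.** The point holds as an internal inconsistency in arm A. With counts below Table 4's limits at D28, Table 4 ends study treatment permanently. Table 5 continues regorafenib for Grades 0-3 and allows it to resume after Grade 4, apart from patients who would need a third dose reduction. This rests on one assumption: that study treatment means both drugs, which is the plain but undefined reading.

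For Grades 0-3 the conflict is one of opposite instructions and has no length in days. For Grade 4 the gap is 4 to 18 days over the clock starts tried above. The mismatch with section 8.1 is secondary: 2 days, plus an exception attached to one of two reasons of equal length.

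The documents do not allow an estimate of how many patients would be affected. Overall survival by intention to treat and the sample size do not depend on this. Treatment-stop dates, time to deterioration and per-protocol classification can. It should be corrected, but it does not undermine the trial's main comparison.

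**What to change.** Reconcile Tables 4 and 5, and align Tables 5 and 6 with section 8.1. The amended text should state:

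1. which drug or drugs are stopped when counts have not recovered at D28, with study treatment defined;
2. when the 30-day period starts;
3. which table prevails when both apply;
4. whether the clinical-benefit exception covers both durations in section 8.1, and whether that list yields to the tables.

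The limits themselves are for the sponsor to choose; none is proposed here. The same amendment can check the note letters in Table 6, where the 30-day note is attached to the dose cell and the note on the number of reductions to the delay cell; they look transposed. The SAP, still to be written under section 9.3, should say how patients handled under either rule before the amendment are classified for the per-protocol population.

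The cost is a wording amendment and notice to sites. No change to the sample size or the primary analysis is needed.

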6.1 Experimental treatment or procedures

Experimental arm: REGIRI (arm A)

[figure not shown]

Figure 1: REGIRI regimen

The treatment schedule will be as follows:

- Starting on days 1 and 15 of each 28-day cycle, all patients will receive irinotecan as an intravenous infusion over a 90 minute period.

The initial dose of irinotecan will be 120 mg/m².

The dose for the second infusion of irinotecan will be 150 mg/m² over 90 minutes if no diarrhea of grade >1 NCI-CTCAE V 5.0 grading or others toxicities of grade >2 occur.

The dose for the third and subsequent infusions of irinotecan will be 180 mg/m² over 90 minutes under the same conditions as for the 2nd infusion.

- -On days 2–8 and 16–22 of each cycle, all patients will receive Regorafenib 160 mg orally once daily.
- -A chemotherapy course = 15 days, 1 cycle = 4 weeks

Control arm: Stivarga® (Regorafenib) (arm B)

-Regorafenib will be given orally at a dose of 160 mg once daily over 3 weeks then one week off.

1 cycle = 4 weeks

[figure not shown]

Figure 2: Regorafenib schedule

The following products will be used in the study:

- Regorafenib, 40 mg tablets
- Irinotecan, 180 mg/m² IV (20 mg/ml)

ARM A: REGIRI (Regorafenib + Irinotecan)

Irinotecan

See manufacturer's product information (Appendix 8).

Irinotecan will be prescribed by each center and used in its marketed form.

The irinotecan will be diluted in a 5 % glucose solution or a 0.9% sodium chloride solution. The irinotecan will be delivered over 90 minutes as an intravenous infusion.

Regorafenib

For Packaging, List of excipients and Storage: See Investigator's brochure (Appendix 8).

Regorafenib® will be provided by Sponsor as tablets of 40 mg.

The investigational product(s) label will bear sponsor's name, address and telephone number, the EudraCT number, product name, dosage form and strength, quantity of investigational product par container, batch number, expiration date, dosing instructions, required storage conditions and required caution statements and/or regulatory statements as applicable.

Protocole NEXT-REGIRI -Version 6.0 du 09/11/2023

Page 39 sur 86

Receipt, distribution, return and destruction (if any) of the study drug must be properly documented.

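### Arm A's haematological rules order irinotecan reductions although no level is defined below 120 mg/m², and for some low platelet counts Table 4 and section 6.1 point in opposite directions

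*Combined protocol and SAP*

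**What the plan says.** **Escalation (section 6.1).** "The initial dose of irinotecan will be 120 mg/m²". The next step is conditional: "The dose for the second infusion of irinotecan will be 150 mg/m² over 90 minutes if no diarrhea of grade >1", with a second condition that no "others toxicities of grade >2 occur". Then: "The dose for the third and subsequent infusions of irinotecan will be 180 mg/m² over 90 minutes", on the same conditions. The synopsis gives the same three doses.

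**Reduction levels (section 6.3).** Table a is headed "Dose reductions of Regorafenib" and lists 120 mg and 80 mg of that drug. There is no corresponding list for irinotecan.

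**Diarrhoea (section 6.3, Tables 1-3).** No row takes irinotecan under 120 mg/m². For grade 3 diarrhoea in a patient already at that dose, Table 3 says: "Irinotecan is not changed at 120 mg/m² and decrease Regorafenib to 120 mg per day".

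**Blood counts (section 6.3).** The trigger in the second row of Table 4 is "Platelets < 100 000/mm ³" on the day 15 count, whatever the neutrophil count. The actions are a delay and a one-level reduction of irinotecan. Under the nadir paragraph, a first grade 4 neutropenia leads to G-CSF at the next course. If it persists with G-CSF, the "irinotecan dose will be reduced at the dose immediately inferior". A third occurrence ends study treatment.

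**The concern.** The regorafenib tables tell the site what one dose level means by pointing to Table a. The irinotecan rules for low counts use the same kind of instruction but point to nothing, and the lowest irinotecan dose in the text is the one every arm A patient starts on. The diarrhoea tables provide for a patient at 120 mg/m²; the haematological rules do not.

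There is also a disagreement in direction. Section 6.1 decides the next dose by toxicity grade, while Table 4 decides it by an ungraded platelet cut-off. Where the two overlap, one raises the dose and the other lowers it.

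At stake is whether the experimental regimen is the same treatment at every centre for the same blood count. In an open multicentre trial with 39 patients planned per arm, an instruction that cannot be carried out as written, or that two sections answer differently, leaves irinotecan exposure to local interpretation. The safety committee's scheduled review (section 10.3) covers the first two months of treatment in the first twenty arm A patients, which includes the escalation period.

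**Working it through.** The plan gives no figure to reproduce and no arithmetic is needed. The check lists the irinotecan doses and follows the rules for a patient who has received only 120 mg/m².

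**Inputs**
- Irinotecan doses in the extracted text: 120, 150 and 180 mg/m² (section 6.1, synopsis). Levels below 120: none found.
- Escalation is blocked only by diarrhoea above grade 1 or another toxicity above grade 2 (section 6.1).
- Table 4 platelet row: under 100 000/mm³ at day 15, with no grade and no exception at 120 mg/m².
- Re-dosing requires platelets of at least 100 000/mm³ and neutrophils of at least 1500/mm³. The delay runs to day 21, or day 28 at most, and treatment stops permanently if counts are not restored by day 28 (section 6.3, under Table 4).

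**Path 1: low platelets at the first day 15 check.** Only the 120 mg/m² infusion has been given. Treatment waits for recovery. The dose of the second infusion is then:

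| Rule, as read | Second infusion |
|---|---|
| Section 6.1, platelet toxicity not above grade 2 and no diarrhoea above grade 1 | 150 mg/m² |
| Table 4, one level below the dose last given (120) | undefined |
| Table 4, one level below the planned dose (150) | 120 mg/m² |

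One blood count gives three answers, and no sentence chooses among them.

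**Width of the overlap.** The CTCAE platelet cut-offs are not in the documents supplied. Let X be the count at which grade 3 begins. Counts from X up to just under 100 000/mm³ satisfy the section 6.1 condition and also trigger Table 4. The overlap exists for any X below 100 000/mm³. Below X, section 6.1 no longer escalates; what remains is the missing level, not the conflict in direction.

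**Path 2: recurrent grade 4 neutropenia.**
1. Infusion 1 is given at 120 mg/m² and grade 4 neutropenia follows.
2. Grade 4 is above grade 2, so section 6.1 does not escalate. Infusion 2 is taken to be 120 mg/m² with G-CSF. This is an inference: section 6.1 does not state the dose when its condition fails.
3. Grade 4 neutropenia occurs again. The nadir paragraph calls for the next lower dose, and none is listed below 120.
4. The stopping rule does not apply, because it begins at the third occurrence.

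This path needs at least two infusions, so it cannot arise at the first day 15 check.

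**Path 3, for comparison: diarrhoea.** After the first course, Table 1 sets irinotecan at 120 mg/m² for grade 2 or 3. From the third course on, Table 3 keeps a patient already at 120 mg/m² there and reduces regorafenib at the first grade 3 episode. Every outcome is a stated dose or a stop.

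**The case against.** The strongest reply is that Table 4 is meant to be counted from the planned dose. One level below the planned 150 mg/m² is 120 mg/m², which exists. Table 1 fits this pattern, since grade 2 diarrhoea after the first course gives 120 where 150 was planned. One can add that section 6.1 is the default schedule and section 6.3 the specific rule for toxicity, so the specific rule should govern. Both readings are reasonable, and the first would settle the platelet case. But the protocol states neither. Nor does counting from the planned dose rescue the nadir rule: in Path 2 the grade 4 event has itself blocked escalation, so the dose due is 120 mg/m² and the level below is still missing.

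It is also fair to say that 120 mg/m² is never declared a general minimum. That is inferred from three listed doses, from the diarrhoea tables and from the absence of anything lower. Figure 1 is not shown, and the product information in Appendix 8 was not supplied, so the absence is established for the extracted text only.

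Four stronger readings are tempting and should not be drawn:
- **That neither order can be carried out at the first day 15 check.** Only the platelet row of Table 4 can apply then; the nadir order needs a recurrence under G-CSF.
- **That patients would be dosed while platelets are low.** The re-dosing condition excludes this.
- **That a number of affected patients can be given.** The background section reports 20% thrombocytopenia with FOLFIRI plus regorafenib. That is any-grade drug-related toxicity on a different regimen, with no timing, and nothing says what share would arise at 120 mg/m².
- **That the gap between the two instructions can be expressed as a percentage.** One side of the comparison is an undefined dose.

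**Conclusion.** The point holds in limited form. In arm A, two haematological rules call for a lower irinotecan dose without a defined level for a patient at 120 mg/m². Table 4 can reach that position after the first infusion; the nadir paragraph can do so from the second infusion on, in a patient who has not been escalated. For day 15 platelet counts under 100 000/mm³ that are not above grade 2, section 6.1 and Table 4 also disagree on direction, and no precedence is stated.

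This is more than missing detail, because followed as written the rules give an instruction that is either undefined or contradictory. It is confined to arm A patients who meet one of the two triggers, and to the dose they resume after recovery. Its frequency cannot be estimated from the documents. The primary comparison remains overall survival by randomised arm; what is exposed is the consistency of irinotecan dosing and of the toxicity record in arm A.

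The conclusion assumes that the missing figure and appendices define no lower irinotecan level. The conflict in direction further assumes that grade 3 platelet toxicity begins somewhere below 100 000/mm³.

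**What to change.** The sponsor should reconcile section 6.1, Table 4, the nadir paragraph and Tables 1-3 by stating four things:
1. The irinotecan dose levels, in a table beside Table a.
2. Whether a reduction is counted from the dose last given or from the dose planned next.
3. What Table 4 and the nadir paragraph require of a patient already at 120 mg/m².
4. Whether section 6.1 or section 6.3 governs the next infusion when day 15 counts are low.

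The content of each rule is the sponsor's clinical decision, and no dose or rule is proposed here. The cost is one small table and a few sentences in an amendment, with no new data or visits.
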